For planning the sample size for this research, we used Gpower (v.3.1.9.2) software. Sample size was estimated for repeated measures ANOVA with three groups (tDCS, tACS, Sham) and two measurements (pre-treatment vs. post-treatment). Statistical power (SP) was predetermined a priori with a value of SP=0.99 ($\alpha=0,01$) to increase the validity of the subsequent analysis and ensure that we do not miss any statistically significant result.

We based the calculation on the data extracted from the meta-analysis by Zortea et al. (2019), who reported a moderate effect size for reduction of pain levels ($F=0.68$) in chronic non-cancer pain patients using the tDCS montage stimulating M1. These results were obtained after comparing 380 patients receiving active tDCS versus 381 who were given Sham stimulation.

Assuming this moderate effect size and the rest of described parameters (SP=0,99), a total of 21 patients would be large enough to detect statistically significant changes in the whole sample. However, it cannot be ignored the non-despicable drop-out rates of this patient profile, corroborated by the own researchers in previous investigations. Besides, we are interested in assessing the effect size of the tDCS intervention among the different categories or types of chronic pain, just as defined by the ICD-11 (Treede et al., 2015), and that requires to create big enough comparable groups. For these reasons, we decided to recruit a larger number of participants, thus stablishing the sample size in 120 patients with refractory chronic pain.

Concerning this research, pain is defined as refractory, regardless of etiology, when it meets the two following conditions. First, multiple evidence-based biomedical therapies

used in a clinically appropriate and acceptable fashion have failed to reach treatment goals that may include adequate pain reduction and/or improvement in daily functioning or have resulted in intolerable adverse effects. Second, pain persists even after psychiatric disorders and psychosocial factors that could be influencing treatment outcomes have been assessed and appropriately addressed.

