After completing the treatment period, participants are summoned to other two evaluation sessions with the same structure and assessment tools as in pre-treatment phase; in case of the daily measurements, the comparison is made between the average of the pre-treatment period and that of the post-treatment period. Therefore, differences observed between these two time-measurements are considered as index of the treatment efficacy. At the post-evaluation session, participants will also answer some questions about the satisfaction with the treatment and self-perceived usefulness/improvement.

Finally, in order to assess the long-term improvement derived from tES, we will contact participants by phone in order to invite them to a follow-up session six months after finishing the treatment. All questionnaires and sensory tests will be applied in the same way, except for daily numerical rating scale. Differences between these results and those obtained in pre-evaluation and post-evaluation will be analysed.

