(Adams & Turk, 2015; Keefe et al., 2004; Jensen et al., 2011). Thus, these factors must be taken into account when assessing the efficacy of tES intervention and we intend to account them as covariates in statistical analysis.

Changes observed in criteria variables between pre- and post-evaluation must be equal or higher than the 30%, in order to ensure their clinical significance. It means that the improvement observed in self-reported questionnaires and in sensory testing (except for EEG) have to achieve or surpass the 30% of the original outcome. The direction of these differences depends on the specific scale; for example, it is expected a reduction in the global MPI score after treatment, but also a rise in pain thresholds. In the case of EEG, the analysis pre-post treatment are only subjected to the statistical significance. However, changes in brain activity patterns attributed to the tES will be tried to relate with improvement in clinical features.

Although all explained measurements are considered as success criteria of treatment, we selected pain intensity as the primary end point, taken as the average obtained from daily numerical rating scale. In this sense, participants will be classified into responders when they report, at least, a 30% decrease in their pain intensity. The rest of the variables are taken as secondary end points and are also regarded as treatment-efficacy indexes, basically the pain thresholds, life quality, physical functioning, interference caused by pain, pain unpleasantness, sleep quality, depression/anxiety, fatigue, caregiver burden and CPM/TSSP responses.

Table 1: End points of the clinical trial and their respective evaluation instruments

End points		Assessment tools
Primary end point	Pain intensity	Numerical Rating Scale of eleven points (0-10 NRS). Average obtained from daily self-reports during the fifteen days before treatment and the fifteen days after treatment.
Secondary end points	Global severity of chronic pain syndrome	Global and subscales scores of Multidimensional Pain Inventory (MPI).
	Interference caused by pain in daily living	Subscale score of Multidimensional Pain Inventory (MPI). Numerical Rating Scale of eleven points (0-10 NRS). Average obtained from daily self-reports during the fifteen days before treatment and the fifteen days after treatment.

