The main quantitative statistical analyses to assess the efficacy of transcranial electrical stimulation techniques consist of ANOVA-tests of repeated measures with three groups. Time-measures for each of the above-mentioned endpoints are taken as intragroup variables (pre vs. post), whereas intergroup measures refer to the received stimulation or treatment (tDCS vs. tACS vs. Sham). Thus, both clinical variables (for example, pain intensity, fatigue, sleep quality, disease severity and interference) and potential biomarkers (including brain oscillatory activity registered by EEG, CPM and TSSP response) are considered as intragroup variables.

Those covariates which show a significant correlation with clinical outcomes will be also included in their correspondent ANOVA analysis. These potential covariates are basically age, self-perceived stress, social support, catastrophism and medication intake.

All these statistical analyses will be repeated in separated groups of patients, created in the basis of sex, type and duration of chronic pain, among other characteristics. The objective is to assess whether the clinical outcomes depend on sex or diagnosis, as each tES could be more effective for specific diseases.

CPM/TSSP response and EEG pattern observed before the tES application are also regarded as potential predictors of the treatment efficacy. Thus, the pre-treatment indexes of these biomarkers will be used as independent variables in *Linear regression models*, which includes the clinical improvement in each endpoint as dependent measure. The procedure will be repeated with *Logistic regression analysis* establishing the respondent vs. no-respondent categories as dichotomic variable.

For last, we will register and assess the percentage of dropouts with their respective motives, in order to obtain an index of the feasibility of home-based tES approach. Client

satisfaction index and caregiver interview will also include questions about the capability of participants to manage with tES devices, data which will be qualitatively analysed.

8. Chronogram

WORKING PLAN (WP)		3	6	9	12	15	18	21	24	27	30	33	36
TASK	\ MONTH												
WP1. Development and selection of assessment and monitoring tools for refractory chronic pain patients													
Task 1.1.	Review of the literature and identification of the most common and important variables used as outcomes in clinical trials with chronic pain population.												

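### The main efficacy test analyses pre-to-post change without adjusting for the endpoint's pre-treatment value; it is valid, but gives up precision that baseline adjustment could recover at almost no cost

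*Combined protocol and SAP*

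**What the plan says.** Section 7 states that the main quantitative efficacy analyses "consist of ANOVA-tests of repeated measures with three groups". The within-patient factor is time ("Time-measures for each of the above-mentioned endpoints are taken as intragroup variables (pre vs. post") and the between-patient factor is arm: tDCS, tACS or sham. The pre-treatment score is therefore half of the outcome and not a covariate.

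Section 6.1 takes the same view of efficacy: "differences observed between these two time-measurements are considered as index of the treatment efficacy". Section 4 sizes the trial on the same design: "Sample size was estimated for repeated measures ANOVA with three groups (tDCS, tACS, Sham) and two measurements (pre-treatment vs. post-treatment".

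On covariates, section 7 says: "These potential covariates are basically age, self-perceived stress, social support, catastrophism and medication intake". The endpoint's own pre-treatment value is not named, and nothing elsewhere adjusts the arm comparison for it. Pre-treatment CPM, TSSP and EEG do enter regression models, but as predictors of improvement.

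For the primary endpoint the baseline is already collected. Section 6.2 says "we selected pain intensity as the primary end point, taken as the average obtained from daily numerical rating scale", and Table 1 sets the two periods as the fifteen days before and the fifteen days after treatment.

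**The concern.** The pre-treatment value of an endpoint is usually the best available predictor of its post-treatment value. Subtracting it in full, as a change score does, is optimal only when the slope of post on pre equals 1. With equal SDs and rho below 1 the slope is less than 1, so subtraction over-corrects. The error variance is then larger than it need be, and an arm that happens to start with higher pain shows a larger fall without any treatment effect.

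What is at stake is precision, chiefly in comparisons with sham. Section 3 gives sham only 20% of the sample, about 24 of 120, and section 4 acknowledges drop-out without putting a figure on it.

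**Working it through.** **Inputs.** From the documents: 120 patients (section 4), allocated 40/40/20 (section 3), i.e. 48/48/24; two time points; three groups. Not in the documents, so assumed: rho from 0.5 to 0.8 (0.9 as an extra case), equal pre and post SDs unless stated, and a true difference of 0.5 SD for the power illustration.

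**1. The plan's own sample size.** Section 4 reports 21 patients from an effect size of 0.68, alpha 0.01 and "Statistical power (SP) was predetermined a priori with a value of SP=0.99". For the group-by-time test, the non-centrality is f² × N × m/(1 - rho). With f = 0.68, N = 21, m = 2 and rho = 0.5, this is 0.4624 × 21 × 2/0.5 = 38.84. On 2 and 18 df, power is 0.994. N = 20 already gives 0.990, and 21 is the next multiple of three. So 21 reproduces at rho = 0.5. In equal groups, rho = 0.3 would need 27 and rho = 0.7 would need 15. The value 0.5 is inferred from the result; the plan does not state it.

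**2. Equivalence.** With two time points, the group-by-time contrast is the arm difference in (post - pre). Its F equals the one-way ANOVA F on change. A numerical check at 48/48/24 gave 0.63369 both ways.

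**3. Variances, equal SDs.** Per patient, in units of SD²: change = 2(1 - rho); baseline-adjusted = 1 - rho². The ratio is 2/(1 + rho).

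| rho | change | adjusted | ratio | extra patients | 120 analysed as change equals adjusted N of |
|---|---|---|---|---|---|
| 0.5 | 1.00 | 0.75 | 1.333 | 33% | 90 |
| 0.6 | 0.80 | 0.64 | 1.250 | 25% | 96 |
| 0.7 | 0.60 | 0.51 | 1.176 | 18% | 102 |
| 0.8 | 0.40 | 0.36 | 1.111 | 11% | 108 |
| 0.9 | 0.20 | 0.19 | 1.053 | 5% | 114 |

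Simulation at 24/48/48 gave ratios of 1.33 (rho 0.5) and 1.10 (rho 0.8).

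**4. Unequal SDs.** If pre SD = s × post SD, the ratio is (1 + s² - 2·rho·s)/(1 - rho²). At s = 0.8:
- rho 0.5: 0.84/0.75 = 1.12
- rho 0.6: 0.68/0.64 = 1.06
- rho 0.7: 0.52/0.51 = 1.02
- rho 0.8: 0.36/0.36 = 1.00

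The ratio is never below 1, and it equals 1 when s = rho.

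**5. Power, one active arm v sham.** Settings: 48 v 24, true difference 0.5 SD, two-sided alpha 0.05, equal SDs. The SE is sqrt(variance × (1/48 + 1/24)) = 0.25 × sqrt(variance). Power is from the non-central t, using the three-arm error df (117 for change, 116 adjusted).

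| rho | change | adjusted |
|---|---|---|
| 0.5 | 0.51 | 0.63 |
| 0.6 | 0.60 | 0.70 |
| 0.7 | 0.73 | 0.79 |
| 0.8 | 0.88 | 0.91 |

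**6. Chance imbalance.** The SE of the baseline difference at 48 v 24 is sqrt(1/48 + 1/24) = 0.25 SD. With equal SDs, the change estimate moves by (1 - rho) × imbalance, in the opposite direction. A one-SE imbalance shifts it by 0.5 × 0.25 = 0.125 SD at rho 0.5, and by 0.2 × 0.25 = 0.05 SD at rho 0.8. Simulated slopes on imbalance were -0.50 and -0.20 for change, and about 0 for the adjusted model.

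**The case against.** Four objections have force.

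- **The penalty is not a known quantity.** A reader might take 11% to 33% as a property of this trial. The documents do not support that: they give neither rho nor the two SDs. Averaging fifteen daily ratings removes day-to-day noise, so rho could be above 0.8, where the loss is small. A pre SD smaller than the post SD also shrinks the loss over most of the range, to nothing in one case. This stands, and the size has to be given as a range.
- **The planned test is not invalid.** A reader might infer bias from its sensitivity to baseline imbalance. Under randomisation such imbalance averages to zero and type I error is kept. The shift in step 6 is conditional on an imbalance that has happened by chance. This stands.
- **The entry threshold does not make it worse.** A reader might link the imbalance effect to the requirement of pain of at least 5/10 (section 4). That threshold applies to the week before enrolment, whereas the diary baseline is collected afterwards (sections 6.1 and 6.2). Regression to the mean caused by selection affects all randomised arms alike, and the (1 - rho) relation holds with or without a threshold.
- **On the plan's own figures there is room to spare.** A change analysis of 120 matches an adjusted analysis of 90 to 108 at rho 0.5 to 0.8, far above the stated 21. That comfort depends on the effect size of 0.68 being right for this test, which is a separate question. It reduces the urgency but is no reason to discard precision.

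The wording of the covariate list leaves it slightly open, but an open list does not provide for baseline adjustment.

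**Conclusion.** The point holds as one of efficiency. The main test is an analysis of change without adjustment for the endpoint's pre-treatment value. It is valid under randomisation and, in large samples, never more precise than the adjusted model.

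If the SDs are equal, the cost is 33% to 11% more patients for rho 0.5 to 0.8, and 5% at 0.9. If the pre SD is 0.8 of the post SD, it is 12% to 0% for rho 0.5 to 0.8. For one active arm against sham, with an assumed 0.5 SD difference and equal SDs, power rises by about 12 percentage points at rho 0.5 and 3 at rho 0.8. The reading of the plan and the direction of the effect are secure; the size depends on quantities that the documents do not give. The change should be made because it uses data already being collected, not because the planned test would mislead.

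**What to change.** In section 7, for pain intensity and each other continuous endpoint measured before and after treatment, replace the group-by-time test by a linear model of the post-treatment value on arm (three groups), with that endpoint's pre-treatment value as covariate. The arm estimate is the same whether the response is the post value or the change, provided the pre value is in the model, so pre-post differences can still be reported as section 6.1 intends.

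Cost: SAP wording, one degree of freedom per model, and a note in section 4 that the sample size was computed for the repeated-measures ANOVA. No new data, visits or patients are needed.

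This does not alter the chi-square comparison of responders, which rests on percentage change, or the six-month comparison. Which further covariates to include, and the rule in section 7 that admits them by significant correlation, should be settled as a separate point.

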Finally, we will explain the daily assessment plan to patients, which starts at this point (i.e., fifteen days before the treatment onset) and continues until fifteen days after the stimulation sessions have finished. Every day during this period, participants will be requested to complete a brief online survey to track the intensity of their symptoms and obtain a more reliable measure. These questionnaires will be sent to patients by phone message, after getting permission from participants.

Specifically, the daily survey consists of several Numerical Rating Scales (NRS) of eleven points (0-10) which ask about the intensity and unpleasantness of pain, interference, fatigue and medication usage, among others. During treatment period, participants can also report any side effect of stimulation through these questionnaires. For each symptom, we will obtain an average of measures obtained before starting the treatment, other average with measures during the treatment and one last average for post-treatment phase (e.g., fifteen days after finishing the intervention).

Moreover, patients will be given a wristband actigraph which should wear during the whole research period. These devices are capable of detecting the sedentary and activity bouts, as well as the intensity of these last ones, the raw acceleration and the distance walked every day. Besides, actigraphs can also measure the total sleep time, the sleep latency and the awakenings after sleep onset. Thanks to this actigraphy technology, physical functioning and sleep patterns will be effectively daily evaluated.

Thus, by the day of the second evaluation session, we will have already obtained a set of daily measures whose average will serve as a reliable clinical baseline. In this second appointment, as part of the potential biomarkers of chronic pain, we will register the electroencephalography (EEG) of the patients during various conditions (Davis et al., 2017). Firstly, EEG will be assessed during a resting state to capture spontaneous brain

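### The main pre/post ANOVA by default leaves out patients with no post-treatment score, although dropout is expected and unused during-treatment diary scores could reduce the resulting bias

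*Combined protocol and SAP*

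**What the plan says.** - **Dropout is expected.** Section 4 states that "it cannot be ignored the non-despicable drop-out rates of this patient profile". It gives no rate. The only response is to recruit 120 patients instead of the calculated 21.
- **The main analysis has two time levels.** Section 7 specifies a repeated-measures ANOVA with three groups for every endpoint: "Time-measures for each of the above-mentioned endpoints are taken as intragroup variables (pre vs. post".
- **A third diary average exists.** For each symptom in the daily survey, Section 6.2 says "we will obtain an average of measures obtained before starting the treatment, other average with measures during the treatment", followed by one for the fifteen days after treatment. Table 1 and Section 7 use only the before and after averages for efficacy.
- **Nothing else covers missing scores.** Section 7 names no imputation, mixed model, analysis population or sensitivity analysis. Dropouts and their reasons are tabulated as a measure of feasibility.
- **Allocation.** Section 3 gives 40% tDCS, 40% tACS and 20% sham, which is 48, 48 and 24 of 120.

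**The concern.** Recruiting more patients protects power. It does nothing for bias. With two time levels, the group-by-time test is a one-way ANOVA on each patient's change (post minus pre), and a patient without a post value has no change to enter. Those patients may differ from the ones who stay. If poor responders leave more often from one arm, the completers are no longer comparable as randomised.

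The sham arm is the most exposed: losing 5 of its 24 patients removes about a fifth of the control group (5/24 = 21%). Meanwhile, diary scores that say how a leaving patient was doing are already scheduled and play no part in the efficacy test.

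**Working it through.** **1. The plan's own figure.** Section 4 describes the calculation thus: "Sample size was estimated for repeated measures ANOVA with three groups (tDCS, tACS, Sham) and two measurements (pre-treatment vs. post-treatment". Its target is 99% power at alpha 0.01, with an effect size of 0.68, entered as Cohen's f. The correlation is not given; 0.5 is assumed. For the within-between interaction with k = 3 groups and m = 2 measurements:

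λ = f²·N·m/(1 − ρ), df1 = (k − 1)(m − 1) = 2, df2 = (N − k)(m − 1) = N − 3.

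- N = 20: λ = 0.4624 × 20 × 2/0.5 = 36.99, power 0.9902.
- N = 21 (three groups of 7): λ = 38.84, power 0.9939.

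The stated 21 reproduces.

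**2. Is this a power problem?** The dropout rate is assumed to be 10%, 20% or 30%. Completers are 120 × (1 − d) = 108, 96, 84. The calculated need inflated for dropout is 21/(1 − d) = 23.3, 26.3, 30.0, so 24, 27 and 30. On the plan's own inputs the exposure is bias, not power.

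**3. Size of the bias.** Everything here except the NRS scale is assumed, because the documents give none of it. The model compares one active arm with sham. Mean NRS is 7 before, 6.5 during and 6.3 after in sham; the active arm is 0.7 lower during and 1.0 lower after; SD is 1.8. Under the common rule, logit P(dropout) = a + 1.5 × (Y − Y_pre)/SD. Y is the during-treatment score (missing at random, MAR) or the unseen post score (missing not at random, MNAR), and a is set to reach the overall dropout rate.

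- Complete-case estimate: the difference between arms in mean (post − pre) among completers.
- Likelihood estimate: within each arm, post regressed on pre and during in completers, with missing posts predicted, then averaged over all patients.

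Results at 20% dropout, during-post correlation 0.8, correlations with baseline 0.6 (bias in NRS points; negative means the benefit is understated):

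| Mechanism | Complete case | With during-treatment mean | Removed |
|---|---|---|---|
| Completely random | 0.00 | 0.00 | n/a |
| Same response rule and same rate in both arms | 0.00 | 0.00 | n/a |
| Common rule, MAR (sham 25%, active 17%) | −0.087 | 0.001 | 99% |
| Common rule, MAR, half of dropouts have no during scores | −0.087 | −0.024 | 72% |
| Common rule, MNAR (sham 27%, active 16%) | −0.171 | −0.085 | 50% |
| Sham only, MAR | −0.252 | 0.007 | 97% |
| Sham only, MAR, half of dropouts have no during scores | −0.254 | −0.082 | 68% |
| Sham only, MNAR | −0.339 | −0.157 | 54% |

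Over 10% to 30% dropout and during-post correlations of 0.6 to 0.9, the share removed is 96% to 100% (MAR, full diaries), 62% to 85% (MAR, half without during scores) and 31% to 75% (MNAR).

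**4. A second set of assumptions.** With SD 1.5, correlations 0.65 (pre-during), 0.60 (pre-post) and 0.80 (during-post), 19% dropout, and varying strength of dependence on response:

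- common MAR rule: complete-case bias about 0.03 to 0.17;
- sham only, MAR: about 0.1 to 0.3, falling below 0.01 with the during-treatment mean;
- sham only, MNAR: about 0.16 to 0.42, falling to about 0.07 to 0.22.

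**5. Scale.** On these inputs the SD of change is √(2 × 1.5² × 0.40) = 1.34. Completers number 48 × 0.81 = 38.9 and 24 × 0.81 = 19.4. The standard error of one active-sham contrast is 1.34 × √(1/38.9 + 1/19.4) = 0.37. A bias of 0.03 to 0.17 is about 0.1 to 0.5 standard errors; 0.1 to 0.3 is about 0.3 to 0.8.

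**The case against.** **The plan never says it excludes these patients.** True. Section 7 defines no analysis set; the omission is the default behaviour of the named method. Its responder rule could also be read as counting a patient without post data as a non-respondent, but it does not say so, and it governs the chi-square comparison, not the main ANOVA.

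**Stopping stimulation is not the same as losing the outcome.** This stands. A reader might infer that everyone who leaves home treatment falls out of the primary test. The documents do not support that. The primary endpoint is a daily online survey (Section 6.2) with daily phone contact (Section 9), so a patient can stop stimulation and still report. No minimum number of diary days is set, so a partial post-treatment diary can still give an average. The loss concerns patients with no post score at all.

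**The near-complete correction is built into the favourable case.** This also stands. When dropout is generated from the score that the model conditions on, the likelihood estimate must come out unbiased. A reader might infer that the during-treatment scores would remove most of the bias whatever the cause of dropout. Without a known mechanism, that does not follow: under MNAR the share removed can fall to about a third.

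**Blinding makes entirely different dropout rules by arm less plausible.** Fair, though not decisive. The common-rule figures are therefore shown beside the sham-only ones, and no single scenario should be taken as the expected bias. Direction is open too: the sham-only cases work against active stimulation, and non-response dropout concentrated in an active arm would work the other way.

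**Conclusion.** The concern holds in a limited form. The plan predicts dropout, names a main analysis that by default omits patients with no post score, and leaves relevant collected data out of the efficacy test.

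The bias is conditional: about zero if dropout is completely random or follows the same rule at the same rate in both arms. At about 19% dropout and SD 1.5 it is roughly 0.03 to 0.17 NRS points under a common MAR rule, 0.1 to 0.3 if only sham dropout depends on response, and larger under MNAR. The rate, mechanism, SD and correlations are all assumptions.

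The during-treatment average helps only the daily-diary endpoints. MPI, SF-36, HADS, PSQI, MFIS, pain thresholds, CPM, TSSP and EEG have no planned measure during treatment and gain nothing from it. How medication changes are handled is a separate estimand question and is not part of this point.

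**What to change.** For the daily-diary endpoints, including primary pain intensity:

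1. Replace the two-level ANOVA by a likelihood-based mixed model on the pre, during and post averages, with arm, period, arm-by-period and an unstructured covariance. Include all randomised patients in the arm to which they were randomised. Test the arm-by-period contrast at post.
2. State that diary data from patients who stop stimulation stay in the analysis.
3. Add an MNAR sensitivity analysis, for example a delta adjustment that shifts the unobserved post scores by stated amounts, separately by arm.
4. Report the complete-case ANOVA as supportive.

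The cost is a change of analysis wording and slightly more analysis work, with no new data. The new primary model rests on a MAR assumption, which is why step 3 is needed.
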